- K:** Local laboratory values obtained as part of standard of care testing for the index acute myocardial infarction event and before obtaining written informed consent should be used to determine study entry and eligibility for infusion 1. However, if results (for ALT, total bilirubin and / or serum creatinine) are not available, then a blood sample must be obtained for the local laboratory testing.
- L:** **For subjects who received infusion 1 of investigational product  $> 12$  hours and  $< 48$  hours after IV contrast administration:** local laboratory serum creatinine value must be obtained before the infusion for comparison with the local laboratory baseline value and reviewed by the investigator. A blood sample for local laboratory testing to assess dosing eligibility for infusion 2 should not occur earlier than 72 hours following the infusion 1.
- M:** During study conduct, the Independent Data Monitoring Committee (IDMC) may make a recommendation to permit discontinuation of blood sampling at Visit 3 and Visit 4 for local laboratory and / or central laboratory biochemistry testing. If the IDMC so recommends, study investigators will be notified by the Executive Committee chairperson that these routine laboratory assessments are no longer required and eligibility for all subsequent infusions is to be based on clinical assessment (ie, starting with infusion 2 / Visit 3).
- N:** Blood sample is to be taken before the start of infusion. This blood sample must be sent to the central laboratory for study analysis purposes.
- O:** Blood samples are to be collected from all subjects at baseline and Visit 6 (Day 29). Immunogenicity testing will be performed using samples from approximately the first 600 subjects (approximately 300 CSL112 and 300 placebo) and oversight will be provided by the IDMC ([Section 8.1.3.6](#)).
- P:** Blood samples are to be collected from all subjects at baseline and Visit 6 (Day 29). Nucleic acid testing and serology (parvovirus B19) will be performed using samples from approximately 300 randomly selected subjects (approximately 150 CSL112 and 150 placebo).
- Q:** Future biomedical research testing includes samples collected at baseline that are intended for storage and / or future analyses (eg, pharmacogenomics).

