### **8.1.3.1.1.3 Acute Kidney Injury**

If there is an increase from baseline in serum creatinine  $\geq 0.3$  mg/dL (27  $\mu$ mol/L), the subject's serum creatinine value must be retested.

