- Infusions 2 and 3 only: blood sample for central laboratory testing (biochemistry panel).
- AE / SAE monitoring.
- MACE endpoint assessment.

Administer the IV infusions 2, 3, and 4 of investigational product (placebo or CSL112) ([Section 6.2](#)).

At the end of the infusion, perform the following assessments:

- AE / SAE monitoring.
- MACE endpoint assessment.
- Infusion 4 only: blood sample for PK / PD assessment (at selected sites).

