### **8.5.2.3                    Visit 6 (End of Active Treatment Period)**

- Visit 6 (Day 29) is the end of the Active Treatment Period and should occur approximately 7 ( $\pm$  2) days after infusion 4 (or last infusion) of investigational product.
- Prior / concomitant medication review.
- Vital signs.
- Body weight.

- Directed physical examination.
- Pregnancy test (if applicable).
- Blood sample for central laboratory testing (biochemistry panel and hematology, immunogenicity, and parvovirus testing).
- AE / SAE monitoring.
- MACE endpoint assessment.
- Blood sample for FBR (if subject consented).

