11.2.2 Adverse Events of Special Interest (AESI)

The following TEAEs are considered to be of special interest:

- Hypersensitivity : SMQ narrow 20000214 for Hypersensitivity will be used to identify the relevant preferred terms. The following summary tables will be produced.
 - An overview of adverse events related to hypersensitivity
 - Hypersensitivity by PT
 - Hypersensitivity by PT separately for serious and non-serious AEs

- Treatment-related hypersensitivity by PT
- Treatment-related serious hypersensitivity events by PT
- Acute kidney injury (AKI):
 - This AESI is defined based on central laboratory values. Any increase in serum creatinine value of $\geq 27 \mu\text{mol/L}$ (0.3mg/dL) from the baseline serum creatinine during the Active Treatment period will be considered an AESI.
 - Any increase in serum creatinine value of $\geq 27 \mu\text{mol/L}$ (0.3mg/dL) from the baseline serum creatinine on two consecutive occasions during the Active Treatment period will also be summarized.
 - Relevant preferred terms based on MedDRA SMQ Acute Renal Failure, narrow 20000003 will be summarized to provide additional, supportive analyses of kidney safety/injury and will include the following summaries:
 - An overview of AKI events
 - AKI events by PT
 - Serious AKI events by PT
 - Non-serious AKI events by PT
 - Treatment-related AKI events by PT
 - Treatment-related serious AKI events by PT
- Potential hepatic injury (PHI):
 - This AESI is defined based on central laboratory values. Occurrence of either concomitant elevations of $\text{ALT} > 3 \times \text{ULN}$ with $\text{TBili} > 2 \times \text{ULN}$, or $\text{ALT} > 5 \times \text{ULN}$ at any time during the study will be considered an AESI.
 - Potential drug-induced liver injury (DILI) will be adjudicated by the CEC. Number (%) of subjects with a positively-adjudicated event will be summarized. The CEC adjudication process will include both central and local lab results.
 - A supporting table of AESI as described in the first bullet including both central and local lab results.
 - Supporting summaries of hepatic events by PT where events will be identified using the following MedDRA SMQs:
 - Cholestasis and jaundice of hepatic origin (SMQ) [20000009] – Broad

- Hepatic failure, fibrosis and cirrhosis and other liver damage-related conditions (SMQ) [20000013] – Broad
- Hepatitis, non-infectious (SMQ) [20000010] – Broad
- Liver related investigations, signs and symptoms (SMQ) [20000008] – Broad

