11.6 Clinical Laboratory Evaluations

11.6.1 General Considerations for Laboratory Data

The list of planned laboratory parameters to be evaluated in this study is shown in Table 11-1.

Table 11-1 List of Planned Laboratory Parameters

Hematology	Hemoglobin	Hematocrit	WBC counts
	Total platelet count	CBC with differential	
Biochemistry	Alkaline phosphatase	ALT	AST
	TBili	Direct bilirubin	BUN
	Cholesterol ^a	LDL cholesterol ^a	HDL cholesterol ^a
	Creatinine	eGFR (calculated)	Triglycerides ^a
	Indirect bilirubin (calculated)		

- ALT = alanine aminotransferase; AST = aspartate aminotransferase; BUN = blood urea nitrogen; eGFR = estimated glomerular filtration rate; cholesterol = total cholesterol; LDL = low density lipoprotein; HDL = high density lipoprotein; CBC = complete blood count; ALT = alanineaminotransferase; AST = Aspartate aminotransferase.
- ^a Lipid panel test results will remain blinded

With the exception of ALT and Tbili used to identify potential hepatic injury events, analysis of clinical laboratory data will be based on results from the central laboratory. Local laboratory results will be included in data listings. The definition of baseline value given in [Section 8.2.5](#) will be applied when assessing change from baseline. The denominator in calculating any percentage will be the number of subjects with a non-missing, valid result at that time point; for shift tables, the denominator corresponds to the number of subjects with a valid result at both baseline and study visit of interest. The laboratory normal reference ranges will be provided and clinical laboratory test results outside the normal reference range will be flagged in the laboratory data listings.

When quantitative laboratory measurements reported are with qualifiers such as “< lower limit of normal” or “> upper limit of normal”, the numeric portion of the laboratory result will be used for the purpose of summarizing the data; however, the actual result will be presented in data listings.

Quantitative laboratory measurements will be categorized based on a comparison with the relevant reference normal range (SI units) as follows:

- Low: Below the lower limit of the normal range
- Normal: Within the normal range
- High: Above the upper limit of the normal range

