- Categories of absolute change from baseline in serum creatinine defined as \leq baseline value, > 0 to < 27 , ≥ 27 to ≤ 44 , > 44 μ mol/L (> 0 to < 0.3 , ≥ 0.3 to ≤ 0.5 , and > 0.5 mg/dL); number (%) of subjects in each category will be presented. Categorization of change from baseline in serum creatinine will be based SI units (μ mol/L) while conventional units are given for descriptive purposes.
- Number (%) of subjects achieving a threshold rise of ≥ 27 μ mol/L (0.3 mg/dL) one or more occasions as well as on two or more consecutive occasions will be presented
- Categories of increase in serum creatinine including $\geq 1.5 \times$ baseline, $\geq 2 \times$ baseline, $\geq 3 \times$ baseline

- Number (%) of subjects with raw serum creatinine value $\geq 354 \mu\text{mol/L}$ (4.0 mg/dL)
- Decreases in eGFR of 25% or more from baseline at any time
- Supportive data listings of individual subject data meeting the above-mentioned criteria will be generated
- Data listings including subjects with one or more values outside the reference range will be produced

Assessment of Drug-Biologic Interactions:

Incidence of elevations in serum creatinine defined as a change from baseline $\geq 27 \mu\text{mol/L}$ (0.3 mg/dL) will be summarized by concomitant use of ACEI or ARBs where concomitant is defined for this summary as any time during the active treatment period.

11.6.2.2 Hepatic function:

Liver Dysfunction:

The number (%) of subjects experiencing concomitant elevations in ALT $> 3 \times \text{ULN}$ and Tbili $> 2 \times \text{ULN}$ or ALT $> 5 \times \text{ULN}$ will be determined. Incidence rates along with 95% CI s [Newcombe, 1998] will be provided. A plot of TBili versus ALT will be generated.

Assessment of Drug-Biologic Interaction:

The impact on liver function due to potential interactions between CSL112 and statins and PCS K9 inhibitors will be investigated by summarizing the incidence of elevations (ALT $> 3 \times \text{ULN}$ and Tbili $> 2 \times \text{ULN}$ or ALT $> 5 \times \text{ULN}$) in ALT and TBili in the following subgroups:

- No statins and no PCSK9i
- No statins and any PCSK9i
- Low or moderate potency statins and no PCSK9i
- Low or moderate potency statins and any PCSK9i
- High potency statins and no PCSK9i
- High potency statins and any PCSK9i

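### The supplementary two-occasion creatinine summary cannot score a rise first seen at an on-time Visit 6, and has no denominator for subjects who might be sampled only at Visit 6

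*SAP*

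**What the plan says.** SAP 11.2.2 makes AKI an adverse event of special interest, defined as any creatinine rise of at least 27 µmol/L (0.3 mg/dL) from baseline in the Active Treatment Period. On the data source it says "This AESI is defined based on central laboratory values". It then adds that a rise of that size "on two consecutive occasions during the Active Treatment period will also be summarized". SAP 11.6.2.1 plans a parallel table of subjects reaching the threshold on "one or more occasions as well as on two or more consecutive occasions will be presented".

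The sampling comes from the protocol. Section 8.5.2.2 reads "Infusions 2 and 3 only: blood sample for central laboratory testing (biochemistry panel", so there is no scheduled draw at Visit 5. Section 8.5.2.3 schedules the next central sample at Visit 6, which "is the end of the Active Treatment Period and should occur approximately" 7 days after the last infusion. SAP 4.1 runs the period from randomization through Day 29.

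Two further provisions matter. For any rise of 0.3 mg/dL or more, Protocol 8.1.3.1.1.3 says the "serum creatinine value must be retested"; 9.6.2.3 repeats this, and neither names a laboratory or a time limit. In note M to the Schedule of Assessments, the IDMC "may make a recommendation to permit discontinuation of blood sampling at Visit 3 and Visit 4".

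On denominators, SAP 11.6.1 says "The denominator in calculating any percentage will be the number of subjects with a non-missing, valid result at that time point". It gives no rule for an outcome that needs two visits.

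**The concern.** The two-occasion table separates sustained from transient creatinine rises. The infusion contains sucrose, and Protocol 1.4 discusses kidney injury reported with sucrose-containing products. A low count in this table will be read as evidence that rises were transient. Part of a low count may mean only that a second qualifying value could not exist under the sampling schedule.

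There are two routes. The first applies with full sampling: a rise detected at the last scheduled draw has no later scheduled draw inside the window. The second applies only if Visit 3 and 4 draws are stopped: affected subjects then have a single scheduled post-baseline central value. If they are counted as not having a sustained rise, both arms' percentages and the difference between them shrink. The plan's renal non-inferiority margin is set on the absolute difference, so readers are likely to look at that scale.

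**Working it through.** **1. The plan's own figure.** The only AKI rate in the documents is the single-occasion background rate in SAP 4.6.1.2: 0.75 × 3.9% + 0.25 × 10% = 5.425%, which reproduces the stated 5.4%. No rate is given for the two-occasion outcome, and no power or alpha figure rests on it.

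**2. Scheduled occasions.** Post-baseline central draws are at Visit 3 (before infusion 2), Visit 4 (before infusion 3) and Visit 6. The usable consecutive pairs are 3–4 and 4–6. By schedule, a rise starting after infusion 3 or 4 is first seen at Visit 6, and no pair begins there. With Visit 6 alone there is one occasion and no pair.

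**3. Whether the required retest supplies the second occasion.**
- SAP 11.6.1 bases laboratory analyses on central results and sends local results to listings, with an exception only for ALT and total bilirubin. A local retest therefore does not count.
- A retest after an on-time Visit 6 falls outside the period. The 11.6.2.1 bullet carries no period limit of its own, but the SAP modification history says renal function is to be summarized only within the period.
- SAP 8.2.7 puts unscheduled values into worst-case summaries. It does not say whether they count as an occasion.

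**4. How many subjects could be sampled only at Visit 6.** The IDMC review falls when about 20% have completed Visit 6: 0.20 × 17,400 = 3,480. At most 13,920 (80%) could follow a reduced schedule, and fewer in practice because enrollment continues during the review.

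**5. Share of true sustained rises that can be scored.** Let f be the share first seen at Visit 6 and g the share of subjects sampled only at Visit 6. Both are assumptions; neither is in the documents. The scorable share is (1 − g)(1 − f).

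| g | f = 10% | f = 33% | f = 50% |
|---|---|---|---|
| 0 | 90% | 67% | 50% |
| 40% | 54% | 40% | 30% |
| 80% | 18% | 13% | 10% |

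**6. Effect on the table.** Assume true sustained rates of 2% (placebo) and 3% (CSL112), f = 1/3, and equal loss by arm.
- g = 0: 2% × 0.667 = 1.33% and 3% × 0.667 = 2.00%; difference 0.67 points.
- g = 80%, all subjects in the denominator: 2% × 0.133 = 0.27% and 3% × 0.133 = 0.40%; difference 0.13 points.
- g = 80%, only subjects with Visit 3/4 draws in the denominator: 1.33% and 2.00% again, on 0.20 × 8,700 = 1,740 per arm.
- The ratio is 1.5 in every case.

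**7. The denominator effect alone.** Set f = 0 and let 25% of subjects be scorable. That corresponds to uniform enrollment over 38 months with an assumed two-month lag after the 20% point: 0.20 + 2/38 = 0.253. Wald intervals:
- All 8,700 per arm: 0.50% against 0.75%, difference 0.25 points (95% CI 0.02 to 0.48), z = 2.09.
- Evaluable 2,175 per arm: 2% against 3%, difference 1.0 point (0.07 to 1.93), z = 2.11.

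The all-subject denominator shrinks the difference and its upper limit. It leaves the test statistic almost unchanged.

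**The case against.** The strongest reply is that this table is supplementary. The defined AKI event is a single rise, and a rise first seen at Visit 6 counts there. It also counts in the change-from-baseline, fold-increase and eGFR tables. The IDMC's non-inferiority comparison likewise uses any rise up to Day 29. SAP 11.2.2 plans a treatment difference with interval for each event of special interest and states none for the two-occasion summary. All of this stands. A reader might infer that late rises drop out of the renal safety assessment altogether; the documents do not support that.

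A reader might also infer that a Visit 6 rise can never qualify. That is too strong. Infusions may be 5 days apart (Days 1, 6, 11, 16) and Visit 6 may come 5 days after the last, on Day 21, or earlier after discontinuation. Since the SAP's period runs through Day 29, a central retest could then fall inside it. The limitation is for an on-time Visit 6 on scheduled central draws.

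The reduced-sampling route is conditional. The IDMC may recommend a stop; non-inferiority is only a minimum criterion for it, and Protocol 10.3.6.2 lets it be limited to subgroups. The documents do not show that any stop took place.

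Finally, the all-subject denominator is one reading of SAP 11.6.1. A two-visit outcome has no single time point, and the same section requires valid values at both visits for shift tables. Dilution from subjects sampled only at Visit 6 is therefore possible, not established. The reply does not reach the full-sampling route: those subjects have valid values at Visits 3, 4 and 6, so they belong in any reasonable denominator while their late rises cannot enter the numerator.

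**Conclusion.** The point holds within limits. Followed as written on scheduled central draws, the two-occasion summary scores a rise first seen at an on-time Visit 6 as not sustained, although the protocol requires that rise to be retested. This undercount comes from the stated rules and needs no IDMC action. With full sampling, 50% to 90% of sustained rises remain scorable for f between 50% and 10%. If Visit 3/4 draws were stopped for everyone straight after the 20% review, 10% to 18% would be, and whether the percentages fall to match depends on a denominator that the SAP leaves open.

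The understatement concerns absolute rates and the risk difference. With equal loss by arm the ratio is preserved, and in the worked example both intervals exclude zero. A reader might infer that the definition steers the trial toward finding no renal harm; the arithmetic does not show that. The single-occasion AKI outcome is unaffected. The correction is worth making because the table is meant to show persistence and the change is cheap. The values of f, g and the 2% and 3% rates are assumptions.

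**What to change.** Amend SAP 11.2.2 and 11.6.2.1 in three places.

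1. For the two-occasion summary, use as denominator the subjects with at least two scheduled post-baseline central creatinine values from Visits 3, 4 and 6. A retest should not make a subject eligible.
2. Present the one-occasion and two-occasion tables separately for subjects sampled at Visits 3/4 and those sampled only at Visit 6.
3. Add a supporting table among subjects with a Visit 6 value, modelled on the central-plus-local hepatic table already in SAP 11.2.2. In it, the protocol-required retest of a Visit 6 rise counts as the second occasion, whether central or local, within a stated number of days and even if drawn after Visit 6. Show the number of rises without a retest.

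The restriction in item 1 matters because a subject sampled only at Visit 6 would usually gain a second value only after a rise. Suppose 75% are sampled only at Visit 6, 3% of them rise and half of those are confirmed, with 2% sustained among the fully sampled. Per 100 subjects, letting retests confer eligibility gives (0.5 + 1.125) / (25 + 2.25) = 6.0%, against 1.625 / 100 = 1.6% over everyone.

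The cost is SAP wording and a few tables. The restricted denominator is smaller and its interval wider, and the supporting table mixes laboratory sources. No new samples are needed provided local retests are accepted there, because the protocol does not say that the retest is central.

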11.2.3 Serious Adverse Events

The following summaries will be presented by treatment arm, SOC, and PT.

- Treatment-Emergent SAEs
- Study Treatment-Related SAEs
- Treatment-Emergent SAEs with a fatal outcome
- Study Treatment-Related SAEs with a fatal outcome

The following listings will be provided:

- All Treatment-Emergent SAEs
- Treatment-Emergent SAEs with a fatal outcome

11.2.4 Deaths

CEC-adjudicated deaths will be summarized by displaying the number and percentage of subjects within categories of CV and non-CV death. All deaths adjudicated with an undetermined cause of death will be analyzed as CV death. Deaths among screen failed subjects will be listed separately.

11.2.5 Adverse Events Leading to Discontinuation of Study Treatment, Withdrawal from the Study, and Other Significant Adverse Events

The following categories of treatment-emergent AEs will be summarized:

- Treatment-Emergent AEs Leading to Discontinuation of Study Treatment
- Treatment-Emergent AEs leading to Withdrawal from the Study
- Treatment-Emergent AEs Leading to Infusion Interruptions

The following listings will be provided:

- Treatment-Emergent AEs Leading to Discontinuation of Study Treatment
- Treatment-Emergent AEs leading to Withdrawal from the Study
- Treatment-Emergent AEs Leading to Infusion Interruptions

11.3 Adverse Events Meeting Pre-specified Criteria:

Adverse events meeting at least one of the following criteria, as specified by the FDA, in communication with CSL, for identification of potential adverse drug reactions, will be reported by SoC and PT. A separate tabular summary will be generated for each of the four bullets below as well as a combined summary of all AEs meeting the pre-specified criteria:

1. AEs that begin within 24 hours after the start of an infusion
2. AEs that begin more than 24 hours after the start of infusion and reported as at least possibly causally related to the administration of study treatment by the investigator or sponsor. It is noted however that the reference to sponsor assessment of causality is part of the FDA definition but this information is not captured in the clinical database.
3. AEs for which the investigator's causality assessment is missing or indeterminate

4. Exposure adjusted incidence of TEAEs: all AEs, for which the incidence in an active treatment arm exceeds the exposure-adjusted incidence rate in the placebo arm by 30% or more on a relative basis, provided the difference in incidence rates is 1% or more. The algorithm is shown below:

For each PT recorded on the AE page of the eCRF, the following algorithm will be applied to define whether or not the PT in question meets the criterion defined in bullet 4.

$$\text{Incidence Rate (IR)} = \frac{\text{Total Number of Subjects with TEAEs}}{\text{Total Number of Subjects}}$$

$$\text{Exposure Adjusted IR (EAIR)} = \frac{\text{Total Number of TEAEs}}{\text{Total Number of Infusions Administered Across All Subjects}}$$

Therefore the PT will be considered to meet the criterion only if both of the following are true:

$$(\text{CSL112 IR-Placebo IR}) \times 100\% \geq 1\%.$$

$$\left(\frac{\text{CSL112 6g EAIR-Placebo EAIR}}{\text{Placebo EAIR}} \right) 100\% \geq 30\%, \text{ where Placebo EAIR} > 0.$$

If the number of events within the placebo group is 0 (ie, Placebo EAIR = 0), then the PT will be considered to be an adverse drug reaction if $(\text{CSL112 IR-Placebo IR}) \geq 1\%$.

